Transcranial direct current stimulation (tDCS) is a non-invasive method of brain stimulation and an emerging treatment for chronic pain.^{65, 66} Excitatory (anodal) stimulation over the dorsolateral prefrontal cortex (DLPFC) is a common tDCS regimen for treating pain. Transcranial direct current stimulation differs from conventional interventions in that it directly stimulates specific brain regions responsible for cognitive and affective processing similar to those activated during CBT for chronic pain.⁶⁷ Transcranial direct current stimulation involves modulation of cerebral cortex excitability by direct application of low-level electric current to an anode electrode site, the current travels to a cathode electrode site stimulating brain regions that lie in the path of current flow. Studies have shown analgesic effects on reported pain intensity and improvements in quality of life after treatment,⁶⁵ as a result of local and connectivity effects within the pain processing brain network.^{68, 69} Anodal tDCS of the DLPFC modulates both sensory and cognitive-affective networks⁷⁰ and reduces pain by inhibiting the maladaptive allocation of cognitive and attentional resources and, influencing emotional and motivational aspects of pain.⁶⁹ A recent integrated review and meta-analysis reported that anodal tDCS to the DLPFC produced an effect size of -0.54 (95% CI, -0.91 to -0.16).⁷¹ A recent trial of home-based tDCS to the DLPFC demonstrated a 46% reduction in pain scores after 20 sessions.⁷² Due to its dependency on brain state,^{73, 74} tDCS appears to be more efficacious at augmenting effects of a *simultaneous/combined* treatment rather than inducing *de-novo* changes.⁷⁵ For example, larger benefits of CBT on psychological outcomes (e.g., depression) have been observed when administered with tDCS,^{76, 77} although this treatment combination has not yet been examined in a sample with chronic pain.⁷⁸

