Feasibility Study: Eligible participants will be assigned to either culturally adapted mobile CBT + active tDCS to the DLPFC or culturally adapted mobile CBT + sham. For the pilot phase, 10 participants will be enrolled from each racial and ethnic group (non-Hispanic Black, Hispanic, non-Hispanic White), and 5 participants in each group will be allocated to receive active tDCS and 5 to sham tDCS. We will alternate assignment of tDCS location within each group as participants are enrolled using an ABAB design for treatment allocation, separately for each racial and ethnic group. Because this is a feasibility study, blocked randomization and blinding is not necessary, but will be employed in a later study. Participants will complete two 20-minute stimulation sessions per week for 6 weeks. Each week, tDCS sessions will be paired with the mobile CBT program (e.g., core content, practice skills) at a time that is convenient to the participant. Two sessions will not occur within the same 24-hour period. As described above, participants will receive a unique activation code prior to each stimulation session. Each active session will be pre-programmed to deliver 1mA of direct current for 20-minutes; each sham session will be programmed to provide a ramp up to 1mA over a 5 second interval and no current flow for the remainder of the session. tDCS parameters cannot be changed by participants. Adolescents will complete the outcomes measures listed below (e.g., pain intensity, functional disability) and parents will complete measures of SES, anxiety, depression, and their child's medication use at baseline and post-intervention.

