4.3 Study Measures/Observations

Participants in both the focus group and feasibility study will be asked to fill out screening questions as described in the paragraph below.

Demographics: Participants will complete a consent to contact form and, if willing, will complete demographics questions during the screening process to obtain ethnicity, race, and other information needed to target recruitment to meet enrollment goals. If we are unable to confirm diagnosis or other screening information needed to confirm eligibility, study staff will ask the parent/guardian to sign a medical release form to obtain pertinent medical records.

Participants in the feasibility study will complete the outcomes measures listed below (e.g. pain intensity, functional disability) and parents will complete measures of SES, anxiety, depression, and their child's perception of pain and medication use at baseline and post-intervention (Table 2)

Pain intensity and pain interference: The *Brief Pain Inventory-Short Form* (BPI) includes a 4-item pain severity scale.⁸⁷ Participants rate their worst and least pain in the last week, average pain, and current pain.⁸⁸ The BPI pain intensity has good internal consistency in survivors of childhood cancer ($\alpha=0.87$).⁸⁹ This measure includes a body diagram to allow participants to indicate where they experience the most pain. This will be used to inform placement of the anodal tDCS electrode (i.e., right vs. left DLPFC).^{90, 91}

Pain catastrophizing: The *Pain Catastrophizing Scale, Child version* (PCS-C)⁹² is a 13-item self-report measure of overly negative attitudes of pain and it consists of three scales of rumination, magnification, and helplessness. Higher scores indicate more pain catastrophizing.⁹³ This measure has good reliability (Cronbach's $\alpha=0.90$) in a clinical sample of children and adolescents with chronic or recurrent pain.⁹² The *Pain Catastrophizing Scale, Parent version* (PCS-P) is a

modified version of the PCS-C based on parent report of their own catastrophizing related to their child's pain. It assesses the same three factors of rumination, magnification, and helplessness.^{94, 95}

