Intervention feasibility: We will assess feasibility using three primary criteria: 1) proportion of approached survivors who agree to participate in the intervention trial, 2) adherence to interventions parameters (module/session completion, reasons for dropouts), and 3) acceptability of intervention procedures. For the R61 feasibility trial we aim to enroll 30 participants (10 from each racial/ethnic group: non-Hispanic White, non- Hispanic Black, Hispanic). In an ad hoc manner, if fewer than 50% of approach survivors agree to participate, the intervention will not be considered feasible (i.e., if we need to approach more than 60 survivors to enroll 30 for the feasibility trial). A participant will be considered a “completer” if he/she completes at least 75% of all the sessions (4/6 CBT and 9/12 tDCS sessions). The intervention will be considered feasible if at least 60% of the participants are completers. The feasibility will be assessed in the overall sample of 30 using exact 95% lower confidence bound (Clopper-Pearson method). Thus, the intervention will be considered feasible if 23 or more participants complete the intervention with 95% exact lower confidence bounds (0.61, 1.0). In addition, in an exploratory manner we will assess completion rates in each racial/ethnic group to see if differences are observed. We also will assess treatment acceptability. If >50% of participants report the intervention as ‘unacceptable’ the intervention will not be considered feasible as designed.

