Finally, we will estimate preliminary effectiveness of the intervention to inform potential changes to the proposed sample size needed for the larger R33 clinical trial. We will compare mean change scores for pain intensity and functional disability in survivors who received active tDCS vs. sham using a two-sample t-test. Although we will not be powered to detect a statistically significant difference between the groups, we will use the effect estimate to inform power calculations for the R33 clinical trial. If any of the feasibility parameters including 1) participation rate, 2) adherence, or 3) acceptability do not meet our a priori defined feasibility definitions, we will re-engage stakeholders and individuals with lived experiences for input and make adaptions to the interventions based their feedback as well as data we collect from participants related to reasons drop out and unfavorable acceptability. Transition to the R33 phase will be contingent on meeting milestones defined in the Study Timeline. These include: 1) adaptation and tailoring of intervention content, 2) completion of mobile CBT program modifications, and 3) completion of the 6-week feasibility trial of culturally adapted CBT + tDCS.

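### Adjusting the active-versus-sham comparison for baseline uses only data already collected and would usually give R33 planning a more precise estimate than the change-score t-test

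*Combined protocol and SAP*

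**What the plan says.** In Section 9.0, the preliminary-effectiveness paragraph gives one analysis for this contrast: "We will compare mean change scores for pain intensity and functional disability in survivors who received active tDCS vs. sham using a two-sample t-test". It concedes the limits of the comparison ("Although we will not be powered to detect a statistically significant difference between the groups") and states its use: "we will use the effect estimate to inform power calculations for the R33 clinical trial". Nowhere do the documents add a baseline covariate, a term for racial/ethnic group, or a confidence interval for this contrast.

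On size, "For the R61 feasibility trial we aim to enroll 30 participants". Section 4.1 (Feasibility Study) splits these 5 to 5 within each of three racial/ethnic groups, so 15 per arm, and sets the method: "We will alternate assignment of tDCS location within each group as participants are enrolled using an ABAB design for treatment allocation". The same section has adolescents complete the outcome measures, and parents report on themselves and on the child's "medication use at baseline and post-intervention". For pain intensity, Section 4.3 names the Brief Pain Inventory, which "includes a 4-item pain severity scale".

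**The concern.** A change score gives the baseline value a fixed coefficient of one. Unless that happens to match the true regression of post score on baseline, some of any chance baseline difference between the arms stays in the estimated effect. With 15 per arm such differences are not small. ANCOVA estimates the coefficient from the data instead, and the baseline score it needs is already required to form the change score.

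The stake is modest but specific. The comparison is not offered as a powered hypothesis test. Its stated purpose is to inform R33 power, so its precision is what matters.

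**Working it through.** The plan states no SD, correlation, precision or power for this comparison, so it has no figure of its own to reproduce.

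**Inputs.** From the documents: n = 15 per arm (5 in each of three groups). Assumed: post-score SD 1; post SD equal to k times baseline SD; baseline-to-post correlation r; arms exchangeable at baseline; no missing post scores.

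**Size of chance imbalance.** The SD of the baseline difference is sqrt(2/15) = 0.365 baseline SD. The probability that it exceeds 0.5 SD in either direction is 17%. With equal SDs the change score leaves a fraction (1 - r) of it in the estimate, with sign reversed. At r = 0.5, an imbalance of 0.5 SD shifts the estimate by 0.25 SD, and the typical (one-SD) shift is 0.5 × 0.365 = 0.18.

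**Why this is the same loss as the wider interval.** The variance of a change score is 1 + 1/k² - 2r/k = (1 - r²) + (r - 1/k)². The first term is the ANCOVA residual variance. The second is the carried-over baseline part. At k = 1 and r = 0.5 this is 1.00 = 0.75 + 0.25. The shift and the loss of precision must not be counted twice.

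**Expected 95% half-widths.** Here c4(v) is the expected sample SD over the true SD on v degrees of freedom.

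- Change score: t(0.975, 28) × c4(28) × sqrt(1 + 1/k² - 2r/k) × sqrt(2/15), with t = 2.0484 and c4 = 0.9911.
- ANCOVA: t(0.975, 27) × c4(27) × sqrt(1 - r²) × sqrt(2/15) × E, with t = 2.0518 and c4 = 0.9908. E = 1.0187 is the expected cost of estimating the slope under chance imbalance, the mean of sqrt(1 + F/28) with F on 1 and 28 df.

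At k = 1, r = 0.5:

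- Change score: 2.0484 × 0.9911 × 1 × 0.3651 = 0.741.
- ANCOVA: 2.0518 × 0.9908 × 0.8660 × 0.3651 × 1.0187 = 0.655.

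Change in half-width, ANCOVA against change score (minus = narrower):

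| r | k = 0.75 | k = 1 | k = 1.25 | k = 1.5 |
|---|---|---|---|---|
| 0.3 | -31% | 0.877 to 0.721 (-18%) | -10% | -5% |
| 0.5 | -26% | 0.741 to 0.655 (-12%) | -4% | 0% |
| 0.7 | -24% | 0.574 to 0.540 (-6%) | +1% | +2% |
| 0.8 | -24% | 0.469 to 0.454 (-3%) | +2% | 0% |

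With equal SDs, ANCOVA is 0.6% narrower at r = 0.9 and 0.7% wider at 0.95.

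**Ceiling on the loss.** The change score does best when r = 1/k, where the carried-over term vanishes. The width ratio is then (2.0518 × 0.9908 × 1.0187) / (2.0484 × 0.9911) = 1.020. At 15 per arm, ANCOVA's expected loss therefore cannot exceed about 2% under this model.

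**Equivalent sample size, equal SDs.** To match ANCOVA on 30 participants, the change-score analysis would need 43.3, 37.8, 33.6 and 31.9 at r = 0.3, 0.5, 0.7 and 0.8, that is 44, 38, 34 and 32. If only 12 per arm give post scores (an assumption), the half-widths at r = 0.5 are 0.84 and 0.74.

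**Checks.** A simulation with three groups of 5 per arm (6,000 runs) gave 0.739 for the change score and 0.653 for ANCOVA at r = 0.5. Adding racial/ethnic group gave 0.656 when group predicted nothing. A separate variance formula, (1 - r²)(2/15)(1 + 1/26) for ANCOVA, takes the standard error from 0.365 to 0.322 at r = 0.5. It gives width ratios of 0.82, 0.88, 0.94 and 0.995 at r = 0.3, 0.5, 0.7 and 0.9.

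**The case against.** The strongest reply is that nothing in the plan is wrong. The t-test is a valid estimator, the comparison is openly preliminary, and none of the three R33 transition milestones uses it. It feeds only possible changes to an R33 sample size that has already been proposed. The R33 analysis model is not in these documents, so one cannot say which SD its power calculation needs. All of that stands, and it makes this an optional refinement.

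The second reply is that the gain is uncertain, and this also stands. It depends on the SD ratio as well as the correlation. Section 3.3 admits only adolescents with at least weekly pain that interferes with daily life. That could narrow the baseline spread and push the ratio above 1, where the gain shrinks or turns into a slight loss. A reader might infer that ANCOVA is always more precise; the table shows that it is not.

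The third reply is that the estimate stays imprecise either way. At correlation 0.5 with equal SDs, the ANCOVA half-width of 0.65 still exceeds the effect size of 0.54 that Section 2.1 cites from a meta-analysis, if that figure is in outcome SD. This is a reason to carry the interval into R33 planning. It is not a reason to prefer the wider one.

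**Conclusion.** The point holds as a low-priority improvement. Baseline adjustment costs no data and usually narrows the interval: by 3% to 18% at correlations of 0.8 down to 0.3 with equal SDs, and by 24% to 31% if the post SD is 0.75 times the baseline SD. If the post SD is 1.25 times the baseline SD, the result runs from a 10% gain at 0.3 to a 2% loss at 0.8. At 1.5 times, it runs from a 5% gain at 0.3 to a 2% loss at 0.7. These figures rest on assumed correlations and SD ratios, 15 evaluable per arm and exchangeable arms.

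Three stronger readings are tempting, and the documents do not support them. The planned t-test is not invalid. The feasibility conclusion is not at risk, since it rests on participation, completion and acceptability. ANCOVA also does not rescue the estimate from predictable, non-randomised alternation: it handles the measured baseline score only, and neither analysis guarantees an unbiased effect.

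**What to change.** In Section 9.0, replace the t-test sentence with:

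> For each outcome, the active-versus-sham difference will be estimated by ANCOVA of the post-intervention score on arm and baseline score (racial/ethnic group, the allocation stratum, may be included as a factor), and reported with a 95% CI, the residual SD and the baseline-to-post correlation. The difference in mean change scores will be reported as a supporting result. The CI as well as the point estimate will be used when informing R33 power.

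The cost is three sentences and one degree of freedom (28 to 27), or three if racial/ethnic group is included (28 to 25), plus a possible loss of about 2% in interval width in unfavourable cases. Little gain is expected from the group term. No visit, instrument or participant is added. Reporting the residual SD and correlation lets the R33 calculation match whichever analysis model that trial adopts.

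A separate matter to settle under either analysis is that Section 4.3 and Table 2 list no measure called functional disability, although the Brief Pain Inventory paragraph cites two Functional Disability Inventory papers (references 90 and 91). The score to be analysed needs naming.

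### Active and sham are balanced 5:5 within each racial/ethnic group, but the planned t-test leaves those groups out; if mean change differs between them, its standard error is on average too wide

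*Combined protocol and SAP*

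**What the plan says.** Allocation (section 4.1, Feasibility Study; repeated in section 4.2): participants alternate between active and sham "using an ABAB design for treatment allocation, separately for each racial and ethnic group". The resulting cells are fixed in advance: "5 participants in each group will be allocated to receive active tDCS and 5 to sham tDCS". Ten participants per group and three groups give 30 in all, 15 per arm.

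Analysis (section 9.0, on preliminary effectiveness): "We will compare mean change scores for pain intensity and functional disability" "in survivors who received active tDCS vs. sham using a two-sample t-test". No term for racial/ethnic group is mentioned, and no confidence interval is planned for this comparison. The plan accepts that "we will not be powered to detect a statistically significant difference between the groups", and gives the result one use: "we will use the effect estimate to inform power calculations for the R33 clinical trial". It does not say whether that estimate is raw or standardized, or which SD goes with it.

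The only outcome that section 9.0 sets out to examine by group is completion: "in an exploratory manner we will assess completion rates in each racial/ethnic group to see if differences are observed".

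**The concern.** The allocation is stratified and the analysis is not. With equal cells, a group whose scores improve more on average contributes equally to both arms, so its advantage cancels from the active-minus-sham difference. A two-sample t-test does not use that fact. Its pooled SD contains whatever variation lies between the three group means, and its standard error is computed as if that variation could fall unevenly on the arms.

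Two things are at stake. First, the stated uncertainty may be larger than the design delivers. Second, planning R33 around a difference in means needs an SD or a standardized effect as well as a difference, and the t-test supplies only the pooled SD. Whether that SD suits R33 depends on how R33 will be analysed, which the documents do not say.

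The point concerns the groups used in allocation. It is separate from any question of adjusting for the baseline score.

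**Working it through.** **Inputs from the documents.** Three groups, 5 active and 5 sham in each (section 4.1); 15 per arm; two-sample t-test on change scores (section 9.0). The plan gives no alpha, SD, effect size or interval for this test, so it has no figure to reproduce. The allocation arithmetic agrees: 3 × (5 + 5) = 30.

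**Assumption.** Let f be the share of within-arm change-score variance that lies between the three groups. The documents do not give it; 0 to 20% is used here. Participants are taken as independent, with a common within-group variance and the same arm effect in each group.

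**Step 1: true variance of the arm difference.** Group means cancel with complete 5:5 cells, so Var(difference) = 2·sw²/15, where sw² is the within-group variance. With sw = 1, the SD of the difference is √(2/15) = 0.365.

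**Step 2: what the t-test estimates.** Within one arm the expected sum of squares is 14·sw² + 15·sb², where sb² is the variance of the three group means (divisor 3). Dividing by 14, the expected pooled variance is sw² + (15/14)·sb².

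**Step 3: ratio of standard errors.** Since sb²/sw² = f/(1 − f), the ratio of the t-test SE to the correct SE is √[1 + (15/14)·f/(1 − f)]. For f = 10%: √(1 + 1.0714 × 0.1111) = √1.119 = 1.058.

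**Step 4: check by simulation** (100,000 trials per row, within-group SD of 1). SEs are root mean squares.

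| f (assumed) | SE ratio, formula | t-test SE | SE with group term | Trials in which the t-test SE is the smaller |
|---|---|---|---|---|
| 0% | 1.000 | 0.365 | 0.365 | 62% |
| 5% | 1.028 | 0.375 | 0.365 | 39% |
| 10% | 1.058 | 0.386 | 0.365 | 23% |
| 20% | 1.126 | 0.411 | 0.365 | 6% |

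The group term uses 26 residual df instead of 28. The two-sided 5% critical t moves from 2.048 to 2.056, a rise of about 0.3%.

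**Step 5: dropout.** Suppose one arm loses two post-intervention scores from one group, leaving 5/5/3 against 5/5/5. That group's weight in its arm mean falls from 5/15 = 0.333 to 3/13 = 0.231. The unadjusted difference then shifts by about 0.10 times the gap between that group's mean change and the average of the other two. The additive model removes this shift.

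**Step 6: which SD suits R33.** Required sample size is proportional to the variance used in planning.

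- If R33 adjusts for group, the residual variance sw² is right, and the t-test's pooled variance overstates the sample size by the square of the Step 3 ratio: 6%, 12% or 27%.
- If R33 enrols a similar mix and does not adjust, the total variance sw²/(1 − f) is right. Planning on the residual SD would then supply only (1 − f) of the participants needed: 95%, 90% or 80%.

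**The case against.** The strongest reply is that the harm is conditional and small. Everything depends on differences between groups in mean change, and the documents report none. Both arms receive the adapted CBT. Adaptation uses individual tailoring variables and could narrow group differences as easily as widen them. Change scores already remove stable differences in pain level. If f is zero, the group term only costs degrees of freedom. This stands: the protocol's rationale makes group differences plausible, but does not establish them.

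Second, a reader might infer that the effect passed to R33 is too small and that R33 will be oversized by 6%, 12% or 27%. The documents do not support that. Section 9.0 speaks only of an effect estimate. If the raw mean difference is meant, the group term leaves it unchanged with complete 5:5 data. The percentages also require an R33 analysis that adjusts for group, and no R33 model is described. Under an unadjusted R33 analysis the t-test's pooled SD is essentially the right planning value, and substituting the within-group SD would undersize the trial.

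Third, the dilution is minor beside pilot noise. With 28 df the relative sampling error of the SD itself is about 1/√56 = 13%, as large as the most extreme row in the table. For scale, an observed standardized effect of 0.54 (a background figure in section 2.1, not a design input) would have a 95% CI of about −0.19 to 1.27 at 15 per arm. The comparison is declared underpowered, and it is neither a feasibility criterion nor a listed milestone for moving to R33.

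These replies limit the size of the point. They give no reason to leave the allocation groups out of the analysis.

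**Conclusion.** The point holds in conditional form. The design balances on racial/ethnic group and the planned test ignores it. If mean change differs between groups, the t-test's standard error is on average too wide by about 3%, 6% or 13% at f = 5%, 10% or 20%. The true f is unknown, and at zero there is no bias. In any single trial the adjusted standard error may turn out the larger one.

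With complete data the arm difference itself is not biased by the omission. With unequal dropout across groups it could be, and section 9.0 anticipates dropouts. No statement that R33 will be mis-sized follows from the documents, because neither the effect measure carried forward nor the R33 model is specified. That gap should be closed. The feasibility conclusions are unaffected.

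This is a modest improvement in analysis at almost no cost; it does not undermine the trial.

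**What to change.** In section 9.0, replace the two-sample t-test with a linear model of change score on arm and racial/ethnic group (three levels). Report the active-minus-sham difference with its 95% CI, on 26 df if all 30 have post-intervention scores.

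Name this one model. Averaging the three within-group differences and using an SD computed within the six group-by-arm cells is a different analysis: that SD has 24 df, and with missing scores the two approaches weight the groups differently and give different estimates.

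Add a sentence saying which effect measure and SD go to R33, matched to the R33 analysis: the model's residual SD if R33 will adjust for racial/ethnic group; the total SD, ignoring group, if it will not and the mix is similar. Reporting both SDs keeps either choice open.

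The cost is two or three sentences and 2 degrees of freedom, with the small chance penalty shown in the table. Race/ethnicity is already collected at screening, so no new data are needed.

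### The 15-versus-15 active–sham estimate is too imprecise to inform R33 power calculations or changes to the proposed R33 sample size, and nothing limits how far it may move that size

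*Combined protocol and SAP*

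**What the plan says.** Section 9.0 estimates preliminary effectiveness "to inform potential changes to the proposed sample size needed for the larger R33 clinical trial". So an R33 sample size already exists, although these documents do not show it. The analysis is simple: "We will compare mean change scores for pain intensity and functional disability" "in survivors who received active tDCS vs. sham using a two-sample t-test". The plan is candid about its limits ("Although we will not be powered to detect a statistically significant difference between the groups") but the same sentence goes on: "we will use the effect estimate to inform power calculations for the R33 clinical trial".

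The size of the comparison follows from two places. Section 9.0 states: "For the R61 feasibility trial we aim to enroll 30 participants". Section 4.1 states, for each of three racial and ethnic groups: "5 participants in each group will be allocated to receive active tDCS and 5 to sham tDCS". Section 4.2 repeats this allocation. That gives 3 × 5 = 15 active and 15 sham.

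For this estimate the plan mentions no confidence interval, minimum important difference, shrinkage or conservative bound, and no rule for weighing it against the existing R33 size.

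**The concern.** Conceding that a comparison cannot detect a difference does not make its point estimate fit for planning. A power calculation needs a precise or deliberately conservative effect size, and this estimate is neither. Because sample size goes with one over the effect squared, sampling error is magnified. A chance large estimate argues for an R33 that is too small; a chance small one argues for an R33 far larger than needed; one at or below zero gives no usable size. This is sampling error alone. It would remain with an unbiased estimate, whatever the allocation method, blinding or adjustment model.

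**Working it through.** The documents give no R33 sample size, alpha, power or outcome SD, so there is no stated figure to reproduce. Everything below is in SD units.

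**Inputs**
- From the documents: 15 per arm (sections 4.1, 4.2 and 9.0), and a two-sample t-test on change scores (section 9.0).
- Scenario for the true effect: section 2.1 cites a meta-analysis of anodal stimulation to the DLPFC that "produced an effect size of -0.54 (95% CI, -0.91 to -0.16"). It is background, not a planning effect for tDCS added to CBT.
- Assumed: R33 at two-sided 5% and 80% power, 1:1, sized on the pilot point estimate alone.

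**Precision of the pilot difference**
- Half-width = t(0.975, 28 df) × √(2/15) = 2.048 × 0.365 = 0.748 SD.
- Standard error of the standardised difference at 0.54 = √(2/15 + 0.54²/60) = 0.37.
- An observed 0.54 would have an exact 95% CI of −0.19 to 1.26.
- Pilot power at a true effect of 0.54 is 30%, which agrees with the plan's own concession.

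**What this does to sample size**
- n per arm = 2(1.96 + 0.84)²/d² ≈ 15.7/d².
- At d = 0.54: 54 by this formula, 55 with the t correction.
- At the limits of the cited interval: 614 at 0.16 and 19 at 0.91.
- At the limits of the pilot's own interval around 0.54: 10 at 1.26, and no finite number at the other end, because the interval includes zero.

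**Simulation** (400,000 pilots per true effect). Each pilot draws an estimate and sizes R33 on it; R33 is underpowered if its power at the true effect is below 80%.

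| True effect | Estimate not above 0 | Underpowered, all pilots | Underpowered, given estimate above 0 |
|---|---|---|---|
| 0.20 | 29% | 50% | 71% |
| 0.30 | 20% | 50% | 63% |
| 0.54 | 7% | 50% | 54% |
| 0.80 | 1% | 50% | 51% |
| 0.91 | 1% | 48–49% | 49% |

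The last column is close to 0.50 divided by the chance of a positive estimate: 0.50/0.930 = 0.54 at 0.54, and 0.50/0.794 = 0.63 at 0.30.

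At a true effect of 0.54 the middle 80% of pilot estimates runs from 0.07 to 1.05. Among pilots with an estimate above zero, the implied R33 size has a 10th–90th percentile of about 14 to 470 per arm, mean true power is 70%, and 29% of these R33 trials have power below 50%.

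**If scores are missing.** No dropout rate is given. With 12 evaluable per arm the half-width is 0.85 SD, and the conditional figure at 0.54 is 55%.

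**What the pilot says about the SD.** With 28 df the 95% limits are 0.79 to 1.35 times the estimate. Sample size goes with SD², so the factor is 0.79² = 0.63 to 1.35² = 1.83.

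**The case against.** The strongest reply is that the plan says only that the estimate will inform calculations and possible changes to an R33 size that already exists. It does not make this estimate the sole determinant, and R33's design is not in these documents. That is correct. The simulated percentages describe a rule in which the point estimate alone sets the size, and the plan does not state that rule. What remains is that the plan states no other rule, and no limit on how far the estimate may move the existing number.

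Four stronger readings are tempting and do not hold:

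- *That R33 would more often than not be underpowered.* The estimate is nearly median-unbiased, so over all pilots the chance is about a half. It rises above that only among pilots with a favourable estimate, and clearly so only for small to moderate true effects. The conditional figures also depend on the cut-off: at a true effect of 0.30, discarding estimates up to 0.05 rather than 0 raises 63% to 67%.
- *That R33 will be powered from this estimate alone.* The text says inform, as above.
- *That a poor estimate would drop a useful treatment.* The R33 transition milestones in section 9.0 are content adaptation, program modification and completion of the feasibility trial; the feasibility criteria are participation, adherence and acceptability. None is an efficacy result.
- *That the pilot gives the SD reliably.* It gives it more usefully than the effect, but the range of 0.63 to 1.83 in sample size is almost threefold. The correlation is imprecise too: an observed 0.5 in 30 participants has a 95% CI of 0.17 to 0.73.

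**Conclusion.** The point stands in a limited form. The stated use needs precision that 15 versus 15 cannot supply: a half-width of about 0.75 SD, and implied R33 sizes spanning more than thirtyfold (470/14 ≈ 34) in the middle 80% of favourable pilots when the true effect is 0.54. Sizing on the point estimate would give adequate power at best about as often as not.

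The half-width depends only on 15 evaluable participants per arm and the t-test. The R33 figures rest on the assumed 5% and 80%, on 0.54 and 0.30 as scenarios, and on sizing by the point estimate alone. The feasibility conclusions of the trial are unaffected; only the onward use of the effect estimate needs to change.

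**What to change.** In section 9.0, replace the statement on using the effect estimate with:

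> The active–sham difference will be reported with its 95% CI as descriptive and will not be used as the R33 effect size. Any change to the proposed R33 sample size will rest on a minimum important difference fixed before these data are seen, with the pilot informing the SD (using an upper confidence limit), the baseline-to-post correlation and the proportion with usable scores, each reported with its interval.

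The introductory sentence on changes to the R33 sample size should be aligned with this. As an illustration, an 80% upper limit for the SD would be about 1.14 times the estimate if all 30 give change scores.

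The cost is wording, plus agreeing the important difference in advance; no new data or participant procedures are needed. The downside is that the R33 size may be less favourable than one taken from a chance large pilot estimate, and the pilot SD remains imprecise, which is why an upper limit is asked for.
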